#### 10.2.2 Serious Adverse Events (SAE)

A Serious Adverse Events (SAE) is defined as any adverse event that:

- Resulted in death
- Is life threatening
- Requires inpatient hospitalization or prolongation of an existing hospitalization
- Results in permanent impairment of a body structure or body function
- Requires medical or surgical intervention to prevent permanent impairment to body structure or a body function
- Led to fetal distress, fetal death or congenital abnormality or birth defect.

A written report will be provided to the IRB/EC per the IRB/EC's reporting guidelines.

#### 10.2.3 Device Deficiencies or Complaints

All problems/deficiencies related to the neurostimulator's physician programmer and to the urodynamic machine (study equipment) will be documented and reported to the Sponsor but are not to be classified as an adverse event in the absence of a subject harm. However, if there is an adverse event that results from the study equipment failure, user error, or malfunction or any other study specific equipment failure or malfunction, that specific event would be classified as an adverse event and reported. If that failure or harm is not previously identified, it is considered unanticipated.

Since the study procedure includes resetting of the PNS parameters, optimization of pudendal nerve stimulation is not considered adverse events but rather part of the anticipated investigation. However, if the stimulation lead polarity assignment and/or adjusting stimulation current parameters result in patient harm, then this is a study procedure related adverse event further categorized as related to Study Equipment (excluding the neurostimulator's physician programmer or UDT systems).

Study specific equipment failures and malfunctions should also be documented in the subject's medical record.

#### 10.2.4 Classification of an Adverse Event

##### A. Severity of event

The following guidelines will be used to describe severity.

- **Mild** – No major impact to the Subject. Events require minimal or no treatment and do not interfere with the participant's daily activities, when applicable.
- **Moderate** – Events result in a low level of inconvenience or concern to the subject. Moderate events may cause some interference with functioning.

- **Severe** – Substantial disruption to Subject well-being. Events interrupt a participant's usual daily activity and may require intervention. Severe events are usually potentially life-threatening or incapacitating. Of note, the term "severe" does not necessarily equate to "serious".

#### B. Relationship to event

All AEs must have their relationship to study procedure assessed by the clinician who examines and evaluates the participant based on temporal relationship and their clinical judgment. The degree of certainty about causality will be graded using the categories below. In a clinical trial, the study product must always be suspect. However, in this study there is no study product. The study procedure includes standard UDT and a modified PNS. When assessing relationship of the AE to the study procedure the assessing clinician should ask if the UDT and/or the acute PNS caused the AE.

- **Related** – The AE is known to occur with the study procedure, there is a reasonable possibility that the study procedure caused the AE, or there is a temporal relationship between the study procedure and event. Reasonable possibility means that there is clear evidence to suggest a causal relationship between the study procedure and the AE, and other possible contributing factors can be ruled out.
- **Potentially Related** – There is some evidence to suggest a causal relationship or an equally or more likely than not related relationship exists (e.g., the event occurred within a reasonable time after the study procedure). However, other factors may have contributed to the event (e.g., the participant's clinical condition, other concomitant events). Although an AE may rate only as "Potentially Related" upon discovery, the AE can be flagged as requiring more information and later be changed to "Related" or "Not Related", as appropriate.
- **Not Related** – There is not a reasonable possibility that the administration of the study procedure caused the event, there is no temporal relationship between the study procedure and event onset, or an alternate etiology has been established for the event.

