#### 2. Stimulation Visit

The second visit includes completion of the full informed consent form and urodynamic testing with and without stimulation. This visit will be conducted within 4 weeks of the Screening and Enrollment Visit. This visit will be conducted in the clinic/site in person. Before any additional study activities occur, the full study consent form must be completed. Prior to beginning the UDT, a urinalysis will be performed to screen for a UTI and a urine pregnancy test will be performed. Before UDT begins, a prophylactic antibiotic will be administered to the patient to prevent urinary tract infection (UTI). In this visit the neuromodulation settings of the implanted device will be adjusted to deliver acute simulation. At the end of the UDT the settings will be

returned to the previously set therapeutic values. The neuromodulation settings constitute the "dose" and can include the voltage/current amplitude, frequency, pulse width, on time/off time duration and electrode polarity assignments. These parameters are limited by the available ranges of the approved neurostimulation device and will be adjusted during the study by the principal investigator to stay within the safe and comfortable levels for each individual study subject.

3.

The following information will be collected during this visit:

- Stimulation previous and current properties/setting
- Urethral Pressure Profile
- UDT data, including Leak Point Pressure (LPP) with and without stimulation
- Complications

Inspire Medical Systems, Inc. is collaborating with Beaumont on this study. Inspire hopes to use insight gained from this trial to guide the creation of a new implantable neurostimulator for patients with stress and mixed incontinence. We have a data sharing agreement in place with Inspire. They are not the study sponsor. They have provided funding for the study to take place and will receive de-identified results. They may wish to be present at some, or all, of the UDT visits. They may attend in person or remotely, via audio headsets. Their presence at these visits would serve to provide real-time feedback and suggestions to study staff. Participants will have the right to decide whether or not representatives from Inspire may be present at their UDT visit.

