## 7 Study Intervention Description

## 7.1 Study test equipment placement & setting

- 7.1.1 An oral antibiotic will be administered to the patient prior to UDT to reduce the risk of infection. The patient will receive either nitrofurantoin (100mg) or Bactrim Double Strength (80mg Trimethoprim/400mg sulfamethoxazole). Which antibiotic is prescribed will be based on patient known drug allergies and investigator determination.
- 7.1.2 Set up the urodynamic machine equipment per site's UDT operation procedure protocol.
- 7.1.3 Perform setup calibration to confirm proper UDT system function per institution practices. The subject will be asked to perform Valsalva and coughing to establish baseline pressure levels that the physician will intend to achieve during the study.
- 7.1.4 The neurostimulator's physician programmer will be used to program the implanted pulse generator deliver stimulation to the pudendal nerve via the implanted neurostimulator leads.

Note: For the testing, patient may be placed in a reclined, seated or standing position.

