### 8.1.2 Potential Risks Associated with use of an antibiotic

Less Frequent (occurring more than 1% but less than 10% of the time):

- Diarrhea
- Nausea and vomiting
- Cramping

Rare (occurring less than 1% of the time):

- Headache
- Itching
- Rash
- Allergic reaction

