## 8.3 Assessment of Potential Risks and Benefits

The risks to the study subjects result from performing the standard urodynamic test and delivering acute PNS from an already active implantable PNS device. Urodynamic testing is a commonly performed, standard of care, procedure used for assessing urinary incontinence and other voiding dysfunctions. Furthermore, the PNS stimulation parameters are within the allowable ranges of the approved stimulation device.

The following activities will be implemented for risk mitigation:

- Only highly experienced health care professional in the field of clinical urology will be selected to perform this study.
- Only subjects meeting the inclusion and exclusion criteria will be enrolled in the study to minimize any pre-disposition to any potential harms.
- The subject's physiologic status will be continuously monitored during the clinically indicated procedure.
- A prophylactic antibiotic will be administered prior to the urodynamic test.

The investigator or fully trained designated study personnel will always be present to conduct the clinical study and may terminate the study at their discretion based on changes in subject condition and study observations.

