### 10.2.1 Adverse Events (AE)

An Adverse Event (AE) is defined as any untoward medical occurrence in a study subject whether or not considered related to the study device, study procedures or study requirements that is identified or worsens during the study.

Adverse events must be assessed and documented by the investigator at the time of the study procedure visit.

The Investigator should institute appropriate therapeutic and follow-up measures in accordance with good medical practice and record them in the subject's medical history.

All AEs will be captured on the appropriate CRF. Information to be collected includes event description, time of onset, clinician's assessment of severity, relationship to study procedure (assessed only by those with the training and authority to make an assessment), and time of

resolution/stabilization of the event.

Any medical condition that is present at the time that the participant is screened will be considered as baseline and not reported as an AE. However, if the study participant's condition deteriorates at any time during the procedure visit, it will be recorded as an AE.

A list of possible risks associated with the study procedure are included in the section titled "Known potential risks" within this document.

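### The causality question in 10.2.4 B leaves out the protocol-required antibiotic, so the same antibiotic reaction can be graded into or out of primary endpoint 1

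*Combined protocol and SAP*

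**What the plan says.** The antibiotic is part of the protocol for every subject. The Stimulation Visit text in 6.3 states: "Before UDT begins, a prophylactic antibiotic will be administered to the patient to prevent urinary tract infection (UTI"). Step 7.1.1 repeats it: "An oral antibiotic will be administered to the patient prior to UDT to reduce the risk of infection". It has its own row in the Table of Events (6.5).

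Its harms have their own heading, 8.1.2, "Potential Risks Associated with use of an antibiotic", apart from those of the urodynamic test (UDT, 8.1.1) and of acute pudendal nerve stimulation (PNS, 8.1.3). Diarrhea, nausea and vomiting, and cramping are classed as "Less Frequent (occurring more than 1% but less than 10% of the time"). Headache, itching, rash and allergic reaction are put below 1%.

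Section 10.2.1 links this list to the study procedure: "A list of possible risks associated with the study procedure are included in the section titled 'Known potential risks' within this document".

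Section 10.2.4 B, which governs grading, names two components only: "The study procedure includes standard UDT and a modified PNS". It then instructs that "the assessing clinician should ask if the UDT and/or the acute PNS caused the AE". Section 8.3 opens in the same way: "The risks to the study subjects result from performing the standard urodynamic test and delivering acute PNS from an already active implantable PNS device". It mentions the antibiotic only later, as a risk mitigation.

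Primary endpoint 1 (5.2) and the event and subject counts in 10.2 are for study-related adverse events (AEs).

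**The concern.** The study gives each subject three things: an antibiotic, a UDT and acute PNS. The plan states expected harms for all three, but the question that decides relatedness asks about two.

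A clinician who sees a rash plainly due to the antibiotic, and who follows the question literally, would answer that neither the UDT nor the PNS caused it. A harm that the subject would not have had without the study could then be missing from the study-related count, which is one of the two primary endpoints. Another clinician, relying on timing or on the risk list, could grade the same event the other way. With at most 15 subjects, one such difference is visible in the reported percentage.

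**Working it through.** The plan states no AE rate, power or threshold for this endpoint, so there is no figure to reproduce. The check has three parts: a comparison of the sections, a trace of the consequences, and a scale calculation.

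**1. Two routes for one event.** Take a non-serious antibiotic reaction, such as diarrhea or a rash, that starts after the Stimulation Visit.

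| Route | Rule | Grade |
|---|---|---|
| Causality question, 10.2.4 B | Neither UDT nor PNS caused it | points to *Not Related* |
| *Not Related* definition, 10.2.4 B | An established other cause is sufficient | *Not Related* |
| *Related* definition, timing arm, 10.2.4 B | A temporal link with the study procedure is sufficient | *Related* |
| *Related* definition, known-risk arm, read with 10.2.1 and 8.1.2 | The harm is on the procedure's risk list | *Related* |

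The arms of both definitions are alternatives, so the event can satisfy both. The section gives no order of precedence.

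**2. What follows from *Not Related*.**
- The event stays on record: 10.2.1 puts all AEs on the case report form, and 10.2.5 requires documentation whatever the relationship.
- It leaves primary endpoint 1 (5.2) and the study-related counts (10.2).
- If non-serious, it loses the follow-up that 10.2.5 gives to study-related AEs, up to 7 days after the end of the study.
- The final report described in 10.1 includes all AEs reported during the UDT. An event first reported at the 1-week call (6.3) falls outside that wording.

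**3. Scale.** Inputs: n = 15, the maximum in 6.1; p from 1% to 10%, the limits of the band in 8.1.2 for each of its three more common harms.
- Expected affected subjects per harm, n × p: 15 × 0.01 = 0.15 and 15 × 0.10 = 1.5.
- Chance of at least one affected subject per harm, 1 − (1 − p)^15: 1 − 0.99^15 = 14.0% and 1 − 0.90^15 = 79.4%.
- Effect of one misgraded subject who has no other related AE: 1/15 = 6.7 percentage points.

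The first two lines describe whether an event occurs. The documents give nothing from which to estimate how often it would then be graded *Not Related*.

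**The case against.** The best defense is that the plan already lets these events in. Section 10.2.4 B says what the procedure *includes*, which need not be a complete list. The antibiotic is a numbered step of the intervention and is given because of the UDT. Timing alone is enough for *Related*, and 10.2.1 adopts the whole risk list. The endpoint speaks of study-related events, and 10.2 of relationship to the study; neither is expressly narrowed to UDT and PNS. The relationship breakdown in 10.2 might even show a *Not Related* row. All of this stands, and it shows that exclusion is permitted but not forced. It does not settle the grade, because the operative instruction names two causes and the *Not Related* definition remains available. The only grading scale defined is relationship to the study procedure, and the plan never says how that maps to study-related.

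A reader might make three stronger inferences that the documents do not support:
- *That the reported rate is biased low.* It can be too low if events are graded *Not Related*, but the text also supports *Related*.
- *That the attribution could not be repaired because Table 1 has no antibiotic field.* Every subject is to receive an antibiotic, so an event can be regraded from its description and onset without the drug's name. Table 1 lists no AE variables at all, so its silence says little about the safety forms.
- *That 14.0% to 79.4% is the chance of an omission.* It is the chance that an event occurs. The upper figure also uses a limit that the band excludes and the maximum sample size. Cramping overlaps with a UDT risk in 8.1.1, which the present question already covers.

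It is also fair that Section 10 plans no hypothesis test and sets no AE threshold, so no stated decision turns on this count.

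**Conclusion.** The point holds as an inconsistency in the grading rule for a primary endpoint. The causality question in 10.2.4 B conflicts with the risk list that 10.2.1 assigns to the study procedure, and the same antibiotic reaction can be graded either way. When it is graded *Not Related*, endpoint 1 and the study-related counts can be too low and the follow-up for non-serious related events is lost, although the record of the event is kept.

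The size is modest and partly unknown: 0.15 to 1.5 expected affected subjects per more common harm, and 6.7 points on the rate for each misgraded subject with no other related AE. This assumes 15 subjects in the safety population, all given the antibiotic, and true rates within the band in 8.1.2. With fewer subjects, each one counts for more.

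**What to change.** In 10.2.4 B, name the protocol-required prophylactic antibiotic beside the UDT and acute PNS, both in the description of the study procedure and in the causality question. Have the clinician record which component or components are implicated. In 5.2 and 10.2, state that study-related covers all three, which agrees with 10.2.1.

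Two further edits are optional and only for consistency: record which antibiotic was given, and add the antibiotic to the opening sentence of 8.3.

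The cost is a few sentences and a component field on the AE form. No treatment, visit or procedure changes. The reported study-related AE rate may be slightly higher.

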#### 10.2.5 Time Period and Frequency for Event Assessment and Follow-Up

The occurrence of (S)AE may come to the attention of study personnel during study visits, or upon review by a study monitor. All AEs occurring during the study must be documented appropriately regardless of relationship.

The Principal Investigator will record all reportable events with start dates occurring during the acute stimulation visit. All study related AEs will be followed until 7 days after the end of the study.

All SAEs, and UADEs will be followed until the event is resolved or until a final outcome is established by the Principal Investigator, or for no more than 30 days post the end of the study, whichever occurs first.

Device Deficiencies or Complaints related to any of the market released medical devices utilized during the study or during the clinically indicated procedure should follow standard reporting procedures applicable to device user facilities.

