#### 5.2 Primary Endpoints

1. Identification of all study-related adverse events
2. Measurement of the changes in LPP with acute PNS compared to without stimulation

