The purpose of real-time collaboration between study staff and Inspire is to make decisions about the best time points and/or bladder volumes to stop for leak point pressure testing, and whether leak point pressure testing should be repeated with stimulation off if no leaks are elicited with stimulation off. The representatives from Inspire may provide additional guidance, as needed, for troubleshooting and ensuring no important data collection is missed.

4. Follow-Up Phone Call

The third visit will take place by phone and will include assessment of any adverse events which may develop following the Stimulation Visit. This will take place 1 week (+/- 2 days) after the Stimulation visit.

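### Two sentences conflict with the rules governing primary endpoint 1: section 10.2.5 ties AE recording to onset at the stimulation visit, and section 11.6 ties safety reporting to completing the UDT

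*Combined protocol and SAP*

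**What the plan says.** Section 5.2 gives the first primary endpoint as "Identification of all study-related adverse events".

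**Which events are recorded.** Section 10.2.5 contains two adjacent statements. The first is broad: "All AEs occurring during the study must be documented appropriately regardless of relationship". The next is narrow: "The Principal Investigator will record all reportable events with start dates occurring during the acute stimulation visit". Section 6.4 ends the study when the Visit 3 phone call is completed. Section 6.3 says of that call that it "will include assessment of any adverse events which may develop following the Stimulation Visit", and places it one week, plus or minus two days, after the stimulation visit. The table of events in section 6.5 marks AE assessment at both Visit 2 and Visit 3.

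Section 10.2.1 uses both scopes. It defines an AE as one "that is identified or worsens during the study" and says "All AEs will be captured on the appropriate CRF". It also says "Adverse events must be assessed and documented by the investigator at the time of the study procedure visit", and that a baseline condition is handled as follows: if the "condition deteriorates at any time during the procedure visit, it will be recorded as an AE".

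**Which subjects are reported.** Section 10.2 puts every subject who received acute PNS in the safety analysis. Section 10.1 agrees, and states that recipients who do not complete the UDT stay in the safety analysis. Section 11.6 instead describes the collection, analysis and reporting of safety information for eligible subjects completing the UDT in the PNS cycle.

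**The concern.** The study tests no hypotheses (section 10), so the AE counts and percentages are themselves the safety result. One rule decides which events enter the count, and the other decides which subjects enter the denominator. Each is stated in two ways.

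Under the start-date sentence, an event beginning on day 3 is outside the record, although the phone call exists to find it. The protocol anticipates such events: section 8.1.3 lists discomfort, dysesthesia and pain after the procedure ends, and section 8.1.1 lists urinary tract infection (UTI) among the UDT risks. Under the section 11.6 sentence, a recipient who does not complete the UDT leaves the safety report. Section 9.5 allows withdrawal for an AE, so any loss of this kind would tend to lower the reported rate. Staff working from different sections could report different counts from the same data.

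**Working it through.** The plan gives no derived figure to reproduce: the sample size is up to 15 and is not power-based (section 10). The check is mainly a comparison of text.

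**Onset window**

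| Source | Scope |
|---|---|
| 10.2.5, start-date sentence | start date during the stimulation visit |
| 10.2.5, preceding sentence | all AEs during the study |
| 6.4 | study ends at completion of the Visit 3 call |
| 6.3 and 6.5 | AE assessment at the Visit 3 call, covering events after Visit 2 |
| 10.2 | all study-related AEs, no onset limit |

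The period in dispute runs from the end of Visit 2 to the call: 7 − 2 = 5 days to 7 + 2 = 9 days. The start-date sentence refers to reportable events, a term the protocol does not define, so the term cannot settle which scope applies. Section 10.2.5 also says study-related AEs are followed until 7 days after the end of the study. That governs how long an event is followed, not which start dates qualify it for recording.

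The expected number of unrecorded events is (subjects) × (risk) × (share of events starting in the disputed period). The documents give up to 15 subjects and broad risk bands: more than 1% but less than 10% for UTI, and less than 1% for the post-procedure symptoms. They give nothing on the share, so the product cannot be evaluated. It is zero if the share is zero. The discomfort, dysesthesia and pain that section 8.1.3 expects in more than 10% of subjects arise during the procedure and are not affected.

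**Safety set**

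| Source | Subjects |
|---|---|
| 10.2 | all recipients of acute PNS |
| 10.1 | recipients, expressly including UDT non-completers |
| 11.6 | eligible UDT completers |

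Illustration, with assumed inputs: n = 15 recipients, one of whom has an AE and does not complete the UDT; k of the other 14 have AEs; no replacement.

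- Sections 10.1 and 10.2: (k + 1)/n. Section 11.6: k/(n − 1).
- Gap: (k + 1)/n − k/(n − 1) = (n − 1 − k)/[n(n − 1)].
- k = 0: 1/15 = 6.7% (exact 95% interval 0.2% to 31.9%) against 0/14 = 0% (0% to 23.2%), a gap of 14/210 = 6.7 points.
- k = 3: 4/15 = 26.7% against 3/14 = 21.4%, a gap of 11/210 = 5.2 points.

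The intervals at k = 0 overlap widely. The illustration shows only that the reported figure depends on which section is followed.

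**The case against.** The strongest reply is that the narrow sentences exclude nothing. None contains the word only. They can be read as duties for Visit 2, matching step 7.5.2, which has complications and AEs recorded at the end of the test. The Visit 3 duty is stated separately, and most of the text supports the broad scope. Staff who make a call to ask about new AEs will presumably record the answers.

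This disposes of one stronger reading. A reader might infer that section 10.2.1 contradicts itself, but recording deterioration during the visit is a subset of recording worsening during the study. Those sentences are inconsistent in emphasis, not in logic. Likewise, a reader might take the final-report sentence in section 10.1 as limiting AEs to those reported during the UDT. It introduces them as an inclusion, which need not be a limit.

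The reply is weaker for section 10.2.5. The preceding sentence already covers all AEs, so if the start-date sentence is only a minimum, its date condition does no work. It also sits under the heading where staff would look for the recording period.

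On the safety set, it is fair to say that section 11.6 explains why there is no monitoring board, that the analysis sections agree with each other, and that UDT completion is undefined. Step 7.3.8 lets testing end for discomfort or any other investigator reason. A reader might infer that everyone who stops early because of an AE would leave the report. The documents do not support that, since such a subject may count as having completed the test. The conflict itself remains: section 11.6 conditions on completion, and section 10.1 expressly keeps non-completers.

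**Conclusion.** Both conflicts are in the current text and bear on the first primary endpoint. Applied as written, the start-date sentence would leave AEs with onset in the 5 to 9 days between Visit 2 and the call unrecorded, and the section 11.6 sentence would leave out recipients who do not complete the UDT.

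The size of the first is unknown. A reader might combine the UTI risk band with 15 subjects and infer a substantial chance of missing a UTI. The documents do not support such a figure: they give no onset timing, and they do not say whether the band allows for the prophylactic antibiotic. The second may affect few subjects or none. The gap of 6.7 percentage points assumes one non-completer with an AE, no AEs in the other 14 recipients, and no replacement, although section 9.5 permits replacement.

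No sample size, power or hypothesis test is affected. The point should be fixed because the rules as worded can give different AE counts, and the protocol's own dominant rules already show how to align them.

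**What to change.** 1. Amend the start-date sentence in section 10.2.5 so that AEs with onset or worsening from the stimulation visit through completion of the Visit 3 call are recorded. Leave intact that section's existing duty to document all AEs during the study, so the amendment does not narrow it.
2. Reword the two visit-bound sentences in section 10.2.1, on assessment and documentation and on deterioration of baseline conditions, to match.
3. Amend section 11.6 so that safety is reported for all subjects who received acute PNS, whether or not they completed the UDT, as sections 10.1 and 10.2 already provide.

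The cost is a few sentences of protocol text and minor case report form work. The phone call is already scheduled, so no visit is added. The reported AE rate may be slightly higher than under the narrow wording.

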6.4 End of Study Definition

The end of the study is defined as completion of Visit 3: Follow-Up Phone Call.

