## 6.5 Table of Events

Activities	Visit 1: Screening and Enrollment Phone visit	Visit 2: Stimulation Visit Within 4 weeks of Visit 1	Visit 3: Follow-Up Phone Call 1 week +/- 2 days from Visit 2
Phone Consent	X		
Eligibility	X		
Medical History	X		
Urinary Incontinence History	X		
Neurostimulator Data	X		
Full Informed Consent		X	
Urinalysis		X	
Pregnancy Test 		X 	
Urodynamic Equipment Setting		X	
Stimulation Setting/Programming		X	
Antibiotic		X	
Urodynamic test with & without acute PNS		X	
UPP (optional)		X	
Adverse Event Assessment		X	X
Study Exit			X

For women of childbearing potential

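### The start-date sentence in 10.2.5 ties AE recording to the stimulation visit, which is inconsistent with AE capture running through the Visit 3 call

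*Combined protocol and SAP*

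**What the plan says.** Several sections of the combined protocol and SAP describe AE capture through the Visit 3 call:

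- **6.3**, on the follow-up call one week (plus or minus 2 days) after stimulation: it "will include assessment of any adverse events which may develop following the Stimulation Visit".
- **6.5**: the row "Adverse Event Assessment" is marked at Visit 2 and at Visit 3.
- **6.4**: "The end of the study is defined as completion of Visit 3: Follow-Up Phone Call".
- **10.2.5**, first paragraph: "All AEs occurring during the study must be documented appropriately regardless of relationship".
- **10.2.1**: an AE is one that is "identified or worsens during the study", and all AEs go to a CRF with their time of onset.
- **10.2**: the safety summary counts all study-related AEs and sets no onset limit.

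Other sentences are worded around the stimulation visit:

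- **10.2.5**, second paragraph: "The Principal Investigator will record all reportable events with start dates occurring during the acute stimulation visit".
- **10.2.1**: "Adverse events must be assessed and documented by the investigator at the time of the study procedure visit".
- **10.2.1**, on a condition already present at screening: if the participant's "condition deteriorates at any time during the procedure visit, it will be recorded as an AE".
- **10.1**: the final report is described as including the AEs and complications reported during the urodynamic test.

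The term 'reportable' is not defined, and no sentence says which wording governs.

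**The concern.** Section 10.2.5 is where site staff will look for the AE time period, and its two paragraphs point to different onset windows. One window runs to a call 5 to 9 days after stimulation. The other names a single visit, which the Synopsis expects to last about 90 minutes. The start-date sentence is the only onset rule in that section addressed to the Principal Investigator.

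The first primary endpoint (5.2) is the identification of study-related AEs, without a time limit. The protocol itself anticipates harms that can begin after the visit: urinary tract infection (8.1.1), antibiotic reactions (8.1.2), and discomfort, dysesthesia or pain after the procedure has ended (8.1.3). Someone applying the start-date sentence literally and someone applying the sentence about the whole study would record different sets of these events, and the endpoint count would differ accordingly.

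**Working it through.** The plan gives no figure to reproduce here, so the check is mainly a comparison of texts.

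**1. Onset window under each rule.** The wide rule in 10.2.5 covers the study, and 6.4 ends the study at completion of Visit 3. Visit 3 falls 7 ± 2 days after Visit 2, that is 5 to 9 days. The start-date rule names events that begin at Visit 2.

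**2. Can another sentence settle it?** The 7-day and 30-day periods in 10.2.5 say how long AEs, SAEs and UADEs are followed. They do not say when an event must start in order to be recorded. Section 10.2 counts all study-related AEs, but can count only what has been recorded. No rule of precedence is given.

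**3. How much does each narrow sentence carry?**

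| Sentence | Weight |
|---|---|
| 10.2.5 start-date rule | Main evidence: an onset condition in the section on time period |
| 10.2.1 assessment and documentation at the procedure visit | Supporting: omits the Visit 3 assessment, but does not forbid later documentation |
| 10.2.1 deterioration rule | Weak: concerns conditions present at screening, not new events |
| 10.1 report wording | Weak: the list is inclusive, and 10.2 has no window |

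**4. Which events are affected?** A urinary tract infection is the clearest case. Urinalysis before the test screens for an existing infection (6.3), so an infection caused by the test would be expected to show itself later. That timing is an assumption, because the documents do not give it. Nor do they give the share of antibiotic reactions that start after the visit.

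**5. Size of one omission.** With the maximum of 15 subjects (6.1), all in the safety population:

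- recorded: 1/15 = 0.067, or 6.7%
- omitted: 0/15 = 0%
- difference: 6.7 percentage points in the percent of subjects with an AE

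This is the effect if one subject's only such event is left out. It says nothing about how likely that is.

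**The case against.** The strongest reply is that the sentences can all be obeyed together. The start-date sentence imposes a duty for one visit and does not say that later events are to be ignored. Apart from study exit, AE assessment is the only activity at Visit 3, so reading 10.2.5 as barring post-visit events would defeat the purpose of the call. Section 10.2.4 also gives, as an example of a potentially related event, one occurring within a reasonable time after the procedure. All of this stands, and it shows that the wide window was intended. It does not explain why the section on time period attaches a start-date condition to the investigator's recording duty.

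Two stronger readings are tempting. A reader might infer that AE capture closes at the end of the stimulation visit. The documents do not support that, because nothing expressly excludes later events and several sections provide for them.

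A reader might also take the 1% to 10% band for urinary tract infection (8.1.1) and compute 1 − (1 − p)^15, which gives 14.0% at p = 0.01 and 79.4% at p = 0.10, as the chance of losing a case. Assuming independent subjects, that is the chance that at least one infection occurs. The chance that one goes unrecorded depends also on whether staff follow the narrow sentence, which the documents do not let us estimate. Prophylactic antibiotic is given as well, and the documents do not say whether the band allows for it.

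A fair point about the remedy is that Visit 2 may follow the Visit 1 phone screen by up to 4 weeks. A window opening at Visit 2 would still sit awkwardly with the sentence covering the whole study unless that interval is addressed.

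**Conclusion.** The start-date sentence in 10.2.5 is inconsistent with the preceding rule in the same section, with the end of study in 6.4, and with the Visit 3 assessment in 6.3 and 6.5. Section 10.2.1 adds to this by naming only the procedure visit for assessment and documentation. The finding rests on the text and needs no numerical assumption.

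The consequence is conditional. If the wide wording is followed, nothing is lost. If the start-date rule is applied literally, study-related events that begin after the visit drop out of primary endpoint 1, and in so small a study a single case is visible in the result. The claim that such events are likely to be missed goes beyond the documents. Severity is minor, and confidence that the wording needs correction is high.

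**What to change.** 1. **10.2.5.** Have the Principal Investigator record all AEs with start dates from full consent at the stimulation visit through completion of the Visit 3 call. Delete the undefined qualifier 'reportable'.
2. **10.2.5, sentence on AEs during the study.** Align it by stating that conditions arising between the Visit 1 phone screen and full consent are recorded as baseline history or, if the sponsor prefers, as AEs.
3. **10.2.1.** Have AEs assessed and documented at the stimulation visit and at the Visit 3 call, and let the deterioration rule cover the same window.
4. **10.1, conforming edit.** Replace the reference to events reported during the urodynamic test with the same window.

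The cost is wording in three sections. No visit, assessment or data item is added, because the Visit 3 call already includes AE assessment and the CRF already takes times of onset and resolution.
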